[figure not shown]
05-0-0141

[figure not shown]
CC Protocol #:
PRMC Protocol #: P6557
Medarex Protocol #: MDX010-24

Abbreviated Title: MDX-010 for patients with pancreatic cancer

Treatment of patients with locally advanced and metastatic pancreatic adenocarcinoma with the single agent MDX-010 (anti-CTLA4)

Principal Investigator: [name].¹

Associate Investigators:

Version Date: March 24, 2005
Update Date: March 24, 2005
IRB Submission Date: February 11, 2005

Précis: Patients with inoperable, Stage IV pancreatic adenocarcinoma, will be stratified based on locally advanced or metastatic disease and treated with infusional MDX-010, a human monoclonal antibody (mab) to CTLA-4. Patients will be treated with a maximum of 2 courses of therapy (each course: 3 mg/kg every three weeks x 4). This study is a phase II assessment with overall response as the primary endpoint.

Table of Contents

1.0	INTRODUCTION	4
1.1	Study Objectives	
1.2	Background and Rationale	
2.0	ELIGIBILITY ASSESSMENT AND ENROLLMENT.....	13
2.1	Eligibility Criteria	
2.2	Research Eligibility Evaluation	
2.3	Patient Registration and Treatment Randomization	
3.0	STUDY IMPLEMENTATION	17
3.1	Study Design	
3.2	Drug Administration	
3.3	Treatment Modifications	
3.4	On Study Evaluation	
3.5	Concurrent Therapies	
3.6	Off Study Criteria	
3.7	Post Study Evaluation (Follow Up)	
4.0	SUPPORTIVE CARE.....	23
5.0	DATA COLLECTION AND EVALUATION.....	25
5.1		
5.2	Data Collection	
5.3	Data Safety and Monitoring Plan	
5.4	Response Criteria	
5.5	Toxicity Criteria	
5.6	Statistical Section	
6.0	HUMAN SUBJECTS PROTECTIONS	29
6.1		
6.2	Rationale for Subject Selection	
6.3	Participation of Children	
6.4	Evaluation of Benefits and Risks/Discomforts	
6.5	Consent and Assent Process and Documentation	
7.0	DATA REPORTING	30
8.0	PHARMACEUTICAL INFORMATION.....	33
9.0	ADMINISTRATIVE REQUIREMENTS	35
10.0	REFERENCES	37
11.0	APPENDIX	42

1.0 Introduction

1.1 Study Objective:

[figure not shown]
[figure not shown]
Primary Objective:

[figure not shown]
To assess the clinical response (PR and CR) to MDX-010 as a single agent in patients with locally advanced pancreatic adenocarcinoma.

To assess the clinical response (PR and CR) to MDX-010 as a single agent in patients with metastatic pancreatic adenocarcinoma.

Secondary Objective:

Define the MTD over the range of doses proposed.

2.0 Eligibility Assessment and Enrollment

2.1 Eligibility Criteria:

2.1.1 Inclusion Criteria

- A. Any patient ≥ 18 years of age with a histologic diagnosis of stage IV pancreatic adenocarcinoma that is clinically evaluable, with at least one site of measurable disease.
- B. Patients must be ≥ 3 weeks beyond their last treatment (radiation, chemotherapy, etc.) for pancreas carcinoma and recovered from any serious toxicity experienced during treatment.
- C. Women should be either: post-menopausal for at least one (1) year; surgically incapable of bearing children; or utilizing a reliable form of contraception. Women of childbearing potential must have a negative urine pregnancy test conducted during screening.
- D. Because the risk of a negative influence of this therapy on reproductive processes, men who may father a child must agree to the use of male contraception for the duration of their participation in the trial.
- E. Life expectancy ≥ 3 months.
- F. ECOG Performance Status ≤ 2 .
- G. Biliary obstruction must be effectively drained by endoscopic, operative or interventional means.
- H. Gastric outlet obstruction must be effectively drained by endoscopic, operative or interventional means.
- I. Required values for initial laboratory test:

- WBC $\geq 2500/\text{ml}$
- ANC $\geq 1500/\text{ml}$
- Platelets $\geq 100 \times 10^3/\text{ml}$
- Hemoglobin $\geq 9 \text{ g/dl}$
- Hematocrit $\geq 27 \%$
- Creatinine $< 2.0 \text{ mg/dl}$
- HBsAg negative
- HIV negative
- Anti-HCV non-reactive, or RNA-PCR (-) if reactive.

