2.2.13 Biochemistry

In this study, patients will receive 3 mg/kg MDX-010 antibody intravenously every three weeks. Our experience with MDX-010 in patients with melanoma or renal cell cancer has shown a correlation between severe autoimmunity and tumor response. It has also shown a higher rate of both autoimmune toxicity and tumor response when MDX-010 is administered at repeated doses of 3 mg/kg. Two separate groups of 21-41 patients will be treated with intravenous infusion of MDX-010 at 3mg/kg for all doses. One of the groups will have locally advanced disease, while the other group will have distant metastases. The two groups will be evaluated separately using the same single arm, two-stage phase II design described in Section 5.5.

Four doses will be designated as a course of therapy and evaluations will be conducted at the end of each course, 3 weeks after the 4th infusion. An informal interim evaluation may be performed 3 weeks after the 2nd infusion to rule out rapid disease progression, but the formal evaluation with tumor measurements will be performed approximately 3 weeks after the 4th dose. CT scanning may be performed at any time during protocol implementation in the event that there is clinical evidence of disease progression

Treatment will be limited to 2 courses of therapy. Patients that respond and subsequently relapse will be treated with additional courses of therapy. Patients may come off study at any time if rapid disease progression occurs.

Patients in the locally advanced disease cohort may experience sufficient tumor response that their disease is rendered resectable. If this occurs, these patients will be treated with standard pancreatic resection rendering them NED (no evidence of disease).

3.2 Drug Administration:

MDX-010: All MDX-010 doses will be administered as an intravenous infusion controlled by an infusion pump. For administration, MDX-010 is to be injected into the IV bag and diluted in 0.9% Normal Saline, USP, to a concentration between 0.2 mg/ml and 1 mg/ml as specified in Section 8.1, and should be administered over 90 minutes through an add-on filter set with 1.2 µm air-eliminating filter [REDACTED]

Do not administer as an i.v. push or bolus. If \geq Grade 3 bronchospasm or other hypersensitivity reaction occurs, the infusion should be discontinued and no additional MDX-010 should be administered.

Surgical guidelines

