3.3.1 MDX-010

There will be no intra-patient dose modifications of MDX-010. Patients will discontinue treatment with MDX-010 if they experience an adverse event felt to be possibly or probably related to MDX-010 antibody that meets the following criteria:

- A patient who requires systemic steroid therapy for any reason will not receive further treatment with MDX-010 but will be followed until off study criteria are met.
- Any infusion related reaction of \geq grade 3. Infusion related reactions are defined as acute reactions that develop and resolve within 48 hours of the start of an infusion. This includes reactions that are responsive to therapy within that time frame except for Grade 3 fever that resolves within 48 hours. Exclusions to discontinuing therapy will be made in the presence of an objective response when the toxicity resolves prior to the next infusion.
- Any autoimmune toxicity of $>$ grade 2 that has the potential to be life threatening with continued antibody administration and is not associated with a potential therapeutic response, except rash, vitiligo or asymptomatic autoantibody detection. An autoimmune reaction is defined as an inflammatory process that compromises the function of any organ and is not attributable to another etiology.
- Any autoimmune toxicity (any grade) that does not resolve by the time that additional dosing with MDX-010 is considered. Patients may delay subsequent doses in a course by up to a maximum of 3 weeks while awaiting resolution of an autoimmune toxicity.
- Uveitis or episcleritis that is symptomatic (causing eye pain, photosensitivity, or blurred vision)
- Exclusions to these criteria include inflammation of $<$ grade 4 that is attributable to a local anti-tumor reaction that could potentially be a therapeutic response. This

includes inflammatory reactions at the site of tumor resection or in draining lymph nodes, or in sites suspicious for metastasis.

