3.4.2.9. PBMC (peripheral blood mononuclear cells) sample

Peripheral blood mononuclear cells (PBMC) will be isolated and purified from samples obtained at baseline and after every course, by drawing 75 ml of blood at these times according to the schedule. In addition, 5 ml of serum will be obtained and stored at baseline and at the time of each blood draw.

Schedule								
	On-Study Evaluation						Follow up	
Visit	2	3	4	5	6	7 ⁷		
Day	0	21 ±2d	42 ±2d	63 ±2d	84 ±2d	105 ±4d		Variable ¹
MDX-010 Dose (mg/kg)	3	3	3	3	3	3		
Adverse events	X	X	X	X	X	X		X
	X	X	X	X	X	X		X
Physical examination	X	X	X	X	X	X		X
Assessment for ocular symptoms	X	X	X	X	X	X		X
Vital signs ³	X	X	X	X	X	X		X
Performance Status	X	X	X	X	X	X		X
Ophthalmologic examination**					X			
Pulmonary Function Testing ²								
Diagnostic imaging					X	X		X
Hematology		X	X	X	X			X
Biochemistry		X	X	X	X	X		X
Urinalysis					X			
Urine pregnancy test ⁴	X	X	X	X		X		
ANA ⁵					X			
Antithyroglobulin					X			
Thyroid Function Test ⁶					X			
Blood sample					X			
Infusion of MDX-010	X	X	X	X		X		
Disease Response					X			X

- ¹ 3-month intervals for 1 year, 6-month intervals for 2 years, and 12-month intervals until recurrence of disease
 - ² •²PFT's will be performed if patients develop any clinical sign or symptom suggestive of deterioration of pulmonary function.
 - ³ Vital signs will be monitored every 30 minutes for the duration of the MDX-010 infusion and for one hour following infusion completion, and then routinely unless otherwise indicated.
 - ⁴ A negative urine pregnancy test will be confirmed prior to each dose of MDX-010 in women of child-bearing potential.
 - ⁵ If ANA positive, perform the ENA. If ENA positive, perform the tests indicated in Section 3.4.2.5.
 - ⁶ If abnormal, run full thyroid panel, including Free T3 and Total T4.
 - ⁷ Subsequent Courses (after the first course) will receive MDX-010 every 3 weeks X 4 if the patient is stable or has a partial or mixed response with toxicities of grade 1 or less after the 1st course. Subsequent courses for patients with stable, partial or mixed response, or for patients with complete or partial responses that have relapsed, may be offered.
- ** Additional ophthalmologic exams will be performed if the patient experiences ocular symptoms.

3.6 Off Study Criteria:

Patients may be removed from the study in the following situations:

- Protocol violations
- Disease progression
- Subject withdrew consent
- Lost to follow up
- Death

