Medarex reserves the right to discontinue any study for administrative reasons at any time. If appropriate, reimbursement for reasonable expenses will be made. Authorized physicians must notify ORKAND when a patient is taken off study.

3.7 Post Study Evaluation (Follow up):

Patients will undergo physical examination, including vital signs, blood sampling for hematological and biochemical evaluation and, as clinically indicated, chest radiography, pulmonary function, diagnostic imaging, three weeks following the last treatment, then at three month intervals for 1 year, at 6 month intervals for two years, and then at 12 month intervals or until disease progresses. Prior to termination of participation in the study, each patient will undergo physical examination, diagnostic imaging, and blood sampling for hematological, biochemical, and immune function assessments.

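### Inclusion criterion D ends male contraception when trial participation ends, not at a set time after the last dose, so a man who leaves early can be 21 days or less past an infusion with no stated duty

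*Protocol*

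**What the plan says.** Protocol 2.1.1, criterion D, states that because the therapy may harm reproductive processes, "men who may father a child must agree to the use of male contraception for the duration of their participation in the trial". No interval after the last dose is given there. Nothing else in the supplied text gives one for men; Sections 2.2.7 and 3.4.1.3 deal only with pregnancy testing.

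The length of participation is governed by these sections:

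- **Section 3.1** (in the supplied file this text follows the 2.2.13 heading): "Patients may come off study at any time if rapid disease progression occurs". It also provides an early look: "An informal interim evaluation may be performed 3 weeks after the 2nd infusion to rule out rapid disease progression".
- **Section 3.6:** "Patients may be removed from the study in the following situations", followed by a list that includes disease progression and withdrawal of consent. No minimum time since the last infusion is set.
- **Section 3.7:** follow-up visits come "three weeks following the last treatment, then at three month intervals for 1 year", then "at 6 month intervals for two years, and then at 12 month intervals or until disease progresses". Before leaving there is a closing assessment, "Prior to termination of participation in the study, each patient will undergo physical examination, diagnostic imaging" and blood sampling, but no waiting period.
- **Section 3.3.1:** a patient who needs systemic steroids "will not receive further treatment with MDX-010 but will be followed until off study criteria are met". Stopping treatment is therefore not the same as leaving the study.

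**The concern.** The criterion's reason and its end point do not match. If contraception is required because of what the drug may do, the duty should be timed from the last exposure to the drug. Timed by attendance, it gives the shortest stated cover to the men who leave soonest after an infusion and the longest to those who stay in follow-up.

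In stage IV pancreatic cancer, exit at progression is an ordinary route off study. At stake is whether a man is told at entry that the precaution continues after he leaves. The statistical design is unaffected.

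**Working it through.** **Inputs**

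- Infusions on Days 0, 21, 42 and 63, with a formal evaluation on Day 84 (Protocol schedule table; the visits after Day 0 carry a window of ±2 days).
- Optional informal evaluation 3 weeks after the second infusion, which is Day 42 (Section 3.1).
- First post-treatment visit 3 weeks after the last treatment (Section 3.7).
- A dose may be delayed by at most 3 weeks for autoimmune toxicity (Section 3.3.1).
- SAP 5.9.1 counts events as treatment-emergent up to 70 days after the last dose.

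**Step 1. Time since last dose at exit**

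Gap = exit day − day of last infusion.

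| Exit point | Calculation | Gap |
|---|---|---|
| Day 42 informal evaluation, third dose not given | 42 − 21 | 21 days |
| Day 84 formal evaluation | 84 − 63 | 21 days |
| First Section 3.7 visit | 3 × 7 | 21 days |
| Any exit between on-schedule doses | – | 0 to 21 days |

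The 21 days agrees with the protocol's own 3-week interval. It is nominal. With the visit windows, the Day 84 gap runs from (84 − 2) − (63 + 2) = 17 days to (84 + 2) − (63 − 2) = 25 days. If a dose is being held for the maximum 3 weeks, the gap can reach 21 + 21 = 42 days. So 21 days or less is possible, but it is not an upper limit for every early leaver.

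**Step 2. Does a duty remain after that day?**

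Under criterion D as written, none is stated once participation ends. A man who progresses by the first Section 3.7 visit can complete the closing assessment and leave at about 21 days. A man who stays in follow-up remains covered.

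**Step 3. Effect of a dose-anchored period**

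Added days = max(0, L − gap), where L is the period after the last dose. The documents give no L for contraception. Taking L = 70 from SAP 5.9.1 purely as an assumption:

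| Gap at exit | Added days |
|---|---|
| 17 | 70 − 17 = 53 |
| 21 | 70 − 21 = 49 |
| 25 | 70 − 25 = 45 |
| 42 | 70 − 42 = 28 |
| 70 or more | 0 |

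These figures measure the extra commitment. They do not measure exposure or harm.

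**The case against.** The strongest reply is that the documents never show the drug to be a reproductive risk 21 days after a dose. They supply no half-life, no reproductive data and no count of affected men. On that view D simply uses one end point where another might be preferred. This stands as a limit on size: no harm is demonstrated.

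Second, a period may be stated elsewhere. The consent pages and Section 8 are not in the file. The supplied protocol is also probably not the last version. SAP Table 2, note 4, points to a part C of protocol Section 2.2.7 that is absent here, and the SAP describes PK and HAHA sampling and a second course for subjects with progressive disease that this protocol text does not contain. This also stands, and it makes the fix conditional. It does not alter what D says: D states an end point, so this is not a case of text that is merely missing.

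Third, exit at 21 days is not automatic. Participation is undefined, removal at progression is permitted and not required, and SAP 2.2.1 allows a further course after progression. Serious adverse events are reportable until four weeks after treatment stops (Protocol 7.2), which suggests that contact may continue. All true, but none of these provisions creates a contraception duty. Section 7.2 in fact allows its window to be extended if the drug may not yet be eliminated, so the protocol accepts that drug can persist after dosing stops.

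Fourth, criterion C gives no duration for women. That is missing detail and is not counted as an error here: C sets no early end point, Exclusion F bars exposure in utero, and a pregnancy test precedes each dose.

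**Conclusion.** The concern holds as a minor safety wording point, worth considering. Criterion D rests on the drug's effect but ends with attendance, and the exit rules let attendance end with no minimum time since an infusion. A man leaving early can be 21 days or less past his last dose (nominally 21 at the scheduled evaluations) with no stated duty.

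The conclusion assumes that participation ends when a man goes off study, and that no removed page or later version sets a post-dose period. It makes no claim that 21 days is unsafe, and it applies only to early leavers. Confidence is medium, mainly because of the text that cannot be seen.

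**What to change.** Reword criterion D so that men agree at entry to use contraception throughout participation and for a fixed period after the last dose of any course, whichever is longer, including after going off study. The sponsor should set the period from the drug's elimination. The 70-day window in SAP 5.9.1 can serve as a provisional placeholder only, since it was written for counting adverse events.

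Align the period with anything stated in the consent form, Section 8 or a later protocol version. If a later D already gives one, no change is needed. The same clause can be added to criterion C for consistency.

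The cost is one clause in the eligibility and consent wording, with no extra visits, staff or patients. Early leavers take on a longer commitment, 49 days for a man leaving at 21 days under the placeholder. The clause informs a man at entry; it cannot bind him once he withdraws consent.

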2.1.2 Exclusion Criteria

- A. Pancreatic fistula, biliary fistula, or enteric fistula not controlled with an appropriate drain.
- B. Any other prior malignancy, except for the following: adequately treated basal or squamous cell skin cancer, superficial bladder cancer, carcinoma *in situ* of the cervix, or any other cancer from which the patient has been disease-free for five (5) years or more.
- C. A diagnosis of pancreatic cancer consistent with acinar cell carcinoma, pancreaticoblastoma, malignant cystic neoplasms, endocrine neoplasms, squamous cell carcinoma, as well as Vater and periampullary duodenal or common bile duct malignancies. Patients with pancreatic adenocarcinomas with associated intraductal papillary mucinous neoplasm identified in the specimen will be included in the study since these adenocarcinomas are ductal in origin, and have a similar natural history to all other pancreatic ductal adenocarcinomas.
- D. Active autoimmune disease or history of autoimmune disease (including uveitis and autoimmune inflammatory eye disease).
- E. Active uncontrolled infection, this includes positive results from HIV, HBsAg and anti-HCV.
- F. Pregnancy or nursing: due to the possibility that MDX-010 could have a detrimental effect on the developing immune system of the fetus or infant, exposure in utero or via breast milk will not be allowed.
- G. Any underlying medical condition which, in the opinion of the principal investigator, will make the administration of study drug hazardous or obscure the interpretation of adverse events.
- H. Any concurrent medical condition requiring the use of systemic or topical corticosteroids or the use of immunosuppressive agents (e.g. cyclosporin and its analog, or chemotherapy agents). All corticosteroid use must have been discontinued > four (4) weeks prior to trial entry.
- I. Prior treatment with any anti-CTLA4 mAb.

2.2 Research Eligibility Evaluation: All screening evaluation studies will be completed within 28 days of initiating therapy.

2.2.1 Physical examination

A history and physical examination will be completed during the screening phase. A physical examination will be completed on the day of admission for the first therapy. Information about the physical and neurological examinations must be present in the source documentation at the study site. Significant findings that are present prior to the start of study medication must be included in the Relevant Medical History CRF/Current Medical Conditions CRF. Significant findings made after the start of study medication that meet the definition of an adverse event must be recorded on the Adverse Event CRF.

2.2.2 Vital Signs

Blood pressure (systolic and diastolic), pulse rate, respiration rate, and temperature will be assessed during screening and at baseline for each dose, then every 30 minutes during administration of MDX-010 infusion, and for one hour after administration, and then routinely unless otherwise indicated. Appropriately sized sphygmomanometer cuffs must be utilized for each patient.

2.2.3 Performance Status

Patient performance status will be graded according to ECOG Performance Status criteria (Appendix 1).

2.2.4 Ophthalmologic examination

Ophthalmologic examination will be performed at baseline and at the end of each course and if any ocular symptoms develop. Visual acuity evaluations will be performed during each such assessment. All reports will be filed with the patient's source documentation. Appropriate CRF's must be completed.

2.2.5 Electrocardiograph

A standard 12-lead electrocardiograph will be performed. Upon receiving the interpretation of the electrocardiograph, the investigator will ensure completion of the electrocardiogram CRF indicating all relevant findings. The electrocardiograph tracing with interpretation will be filed with the patient's source documents. Subsequent ECGs will be obtained if clinically indicated.

2.2.6 Diagnostic imaging

Chest, abdominal and pelvic CT or MRI and chest x-ray will be performed at baseline. The most effective diagnostic modality must be employed consistently throughout the study. The same imaging modality, method of assessment, or technique must be used throughout the study to identify any new lesion. Conventional CT and MRI should be performed with cuts of 10 mm or less in slice thickness contiguously.

2.2.7 Pregnancy tests

Women of childbearing potential must have a negative urine pregnancy test conducted during screening and a negative urine pregnancy test within 72 hours prior to Day 0, with results verified prior to dose administration.

